2.1.6. Summary of Background: Veterans with OSA comprise a large population where weight loss may offer substantial benefits to quality of life and reduce risks of morbid events. Despite promising results from efficacy trials of lifestyle-based weight loss programs, we have a limited understanding of weight loss' impact on meaningful outcomes and integration of weight loss into usual care. Veterans with OSA rarely receive weight loss counseling, and existing weight loss offerings have poor accessibility. Our research informs efforts to overcome these gaps using a novel population health approach (Figure 1).

Figure 1. Addressing Gaps in Weight Loss Care for Veterans with OSA

2.1.7. Framework: We designed this pragmatic trial, POWER, with the Triple Aim as our primary framework.³⁶ The Triple Aim provides a system-level model to optimize health system performance by simultaneously addressing three interdependent dimensions: patient experience of care, population health, and per capita health costs (Figure 2). **Experience of Care:** We propose a patient-centered approach to weight loss care among patients with OSA. Our remote intervention reduces geographic barriers and time required to travel and participate in appointments. The self-directed and remote nature of the intervention allows Veterans flexibility, enabling access for those with family and work obligations. **Population health:** Our intervention is independent of Veterans being seen in clinical care and uses administrative data to remotely identify and recruit patients, enabling centralized implementation. Unlike many other remote interventions, our intervention does not rely on Veterans having internet access or tech literacy, as course videos will be available by DVD and/or USB drive in addition to streaming. **Per capita cost:** The course videos for this intervention cost ~\$16, and we will utilize a small number of staff to care for Veterans across multiple regions. We anticipate the intervention to be low-resource per capita. Finally, we acknowledge the Quadruple Aim and consideration of provider work-life.³⁷ Our population health approach addresses weight loss without additional demands on existing providers.

Figure 2. The Triple Aim

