3.0 Objectives

In POWER, we propose a pragmatic hybrid type I randomized control trial of adding the lifestyle intervention to usual care for Veterans with OSA and obesity. We will take a population health approach by proactively offering weight loss and delivering the lifestyle intervention independent of provider referral or resources. Our primary focus is effectiveness for meaningful outcomes, and we will also assess determinants of widespread implementation of our intervention, alternative guideline-based treatments for OSA and obesity, and the achievement of patient-centered outcomes.⁴³

Primary Aim: Test the effectiveness of a proactively delivered and pragmatic weight loss intervention to improve sleep-related quality of life and weight among patients with OSA and obesity.

Secondary Outcomes and Measures:

1. Additional effectiveness outcomes including changes in sleep symptoms, cardiovascular risk scores, blood pressure, and physiologic OSA severity (AHI)
2. Implementation outcomes informed by the RE-AIM framework including Reach, Adoption, Implementation (including costs/budget impact analysis), and Maintenance

Hypotheses:

H1 (Primary Hypothesis): Lifestyle intervention will lead to greater weight loss and improvement in sleep-related quality of life at 12 months relative to usual care.

H2a (Secondary Hypothesis): Lifestyle intervention will lead to greater improvement in secondary outcomes relative to usual care.

H2b (Secondary Hypothesis): Self-directed lifestyle intervention will lead to lower 12-month AHI relative to usual care.

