5.2 Recruitment Methods

5.2.1 Enroll Veterans nationwide with OSA and obesity

5.2.2 Identify eligible participants through CDW:

We apply CDW algorithms to identify potentially eligible participants and verify eligibility via chart review using approved platforms including JLV/CAPRI (see Table 4, Section 5.4).

5.2.3 Screening for index weight/BMI:

Using CDW, we will identify Veterans with prior sleep study (CPT 95800, 95801, 95806, 95810, 95811), with associated diagnosis of OSA, an eligible BMI (index weight), a weight measurement indicating obesity (to minimize spurious inclusion), and who are likely free of exclusionary conditions searchable in CDW. We will retain pertinent socio-economic, demographic, and healthcare utilization data on all individuals identified to inform our organizational partners about the potential reach of the program.

5.2.4 Oversampling:

We may oversample:

- Women – our goal is to enroll approximately 30% of the cohort being female;
 - As we approached a third of our randomization goal, we observed that approximately 25% of enrollees were female. In order to increase our target oversampling, we may evaluate and re-mail an invitation to women. Our criteria include female non-responders who had an initial mailing at least 2 weeks prior and have an end of window greater than 2 weeks away.
- Minorities, if necessary, to have a balanced proportion of the cohort

5.2.5 Research invitation:

Using patients identified through CDW, we will mail and/or email invitations to enough Veterans to enroll 696 subjects. The invitation will contain:

- Flyer;
- Invitation Letter;
- Information Sheet;
- Opt in/out Post Card;
- Email decryption instructions;

We may pursue the option of posting the packet on the HSR&D public website for easy access in the future.

In order to meet our target recruitment timeline, we may re-mail and/or re-email to non-responders if they have not replied two weeks or more after initial mailing/emailing.

Once we meet our randomization goal, we will inform participants who have opted-in but are not yet randomized that enrollment is closed.

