5.3 Informed Consent and Randomization

5.3.1 Telephone screen, consent, and baseline assessment:

For those potential participants who do not return an opt-out postcard within 2 weeks (as well as those who return the opt/in card and those that opted in via Qualtrics), a research coordinator may telephone to:

- Describe study and answer questions.
- Assess eligibility, including potential exclusions for safety. (Section 5.4)
- Obtain consent under a waiver of documentation of written informed consent.
- Administer baseline surveys; or participant may complete online versions or paper copies and return via postage-paid mail.

5.3.2 Medical clearance:

For individuals who consent at the telephone screen and have fulfilled safety requirements, study staff will send a secure email to the patient's primary care provider to inform them of their patient's participation and to alert us if there is any reason that their patient should not participate. If the primary care provider does not respond after four days, we will send a second email. If no response to the second email, we will send a third email informing the PCP that we will enroll the individual in three business days unless they contact us otherwise. We will inform interested participants if their provider responded that this intervention is not appropriate.

As outlined in section 5.5.6, a subset of POWER subjects will be selected to have a single-night diagnostic home sleep study at 1 year. Among those selected for this sleep study, study staff will send a secure email to the patient's primary care provider and, if available, their sleep specialist. This email serves to inform their providers of their patient's participation in a single-night sleep study, asks if they have any concerns about their patients' participation in this diagnostic sleep study, and states that we will proceed with the sleep study unless the specialist contacts us within five business days. As diagnostic sleep studies, proposed in this trial, are often used as part of usual care to diagnose OSA and observe changes in patients' OSA severity over time, we do not expect that many providers will object to participation.

5.3.3 Randomization:

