POWER staff will randomize each participant into the usual care or intervention group at a ratio of 1:1. Participants must have PCP clearance and completed baseline surveys before randomization can occur. Randomization should occur no more than sixteen weeks after the date of the index weight. After sixteen weeks we may ask the participant to return to the primary care clinic for a new index weight if still not randomized. We will notify participants of their randomization group via mail and/or email. The mailing will include a weight scale for all participants and the additional materials (DVDs and/or USB drives, instructional handouts, GLB curriculum, Calorie King Fat & Carbohydrate Counter, and paper tracking booklets) for intervention participants.

5.3.4 Stratification: Given three stratifying variables of BMI category (strata: 30-34.9 vs. 35-44.9 kg/m²), physiologic OSA severity (moderate to severe as defined by interpreting physician or apnea hypopnea index ≥ 15 events/hour vs. otherwise) and sleep related impairment (PROMIS Sleep Impairment T-score ≥ 60 vs. T-score < 60) there will be 8 strata. Stratification may help prevent covariate imbalance between groups.

5.3.5 Continuation of usual care: We will provide all control patients with the same weight scale as we provide to intervention patients. All participants will continue to receive standard care for OSA from their usual primary care and sleep providers. We chose usual care only for our control group because pragmatic RCTs are most useful in testing interventions in real-world settings and addressing the question “how does the intervention compare to what we are doing now?” We believe that including an alternate approach such as an attention control condition would undermine the purpose of this trial. Our study will not interfere with ongoing patient care, including referral to MOVE!, PAP prescriptions, or other sleep treatments. To protect external validity, no participant will be instructed not to seek weight loss or OSA treatment. We will include all participants in the intent to treat analysis. We will monitor electronic health record (EHR) data for participation in MOVE! and patient report for participation in non-VA weight loss programs. We will monitor PAP use through VA approved manufacturer-specific portals (Phillips Encore, ResMed AirView) as well as VA approved data management systems (e.g. Somnoware).⁵³

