Immediately after randomization, the study staff will mail a weight scale to all participants and the additional materials (DVDs and/or USB drives, instructional handouts, GLB curriculum, Calorie King Fat & Carbohydrate Counter, and paper tracking booklets) to intervention participants. Coaches will then call participants to confirm package receipt, review materials and instructions, confirm understanding, and address any questions. Similar to the E-LITE self-directed intervention, we will deliver the intervention's core curriculum in the first 3 months using the 12-session GLB videos available via DVD, USB drive, or online streaming per Veteran preference. Veterans will also be able to choose to engage in self-monitoring of weight and activity using a web-based program (MyFitnessPal) or paper GLB booklets. A lifestyle coach will reach out every other week with messages through MyFitnessPal or text message reminding participants to watch the designated GLB video session and continue self-monitoring. We will instruct participants to contact the lifestyle coaches via MyFitnessPal messaging or phone if they have questions or would like behavioral counseling. Participants are asked to watch one ~25-minute video session a week. As recommended by guidelines, the main objective of the core curriculum (months 1-3) is to facilitate gradual weight loss through successive and progressive changes in diet and physical activity and behavioral skills training. Months 4-12 focus on continued self-directed/monitored gradual weight loss and maintenance. Participants will have access to the lifestyle coach for all 12 months of the intervention.

Self-monitoring is key to successful behavioral weight-loss interventions.⁵⁸ E-LITE results support a positive relationship between frequency of self-monitoring and weight loss.⁵⁹ We will encourage participants to continue self-monitoring through MyFitnessPal or paper trackers beyond the 3-month core intervention. The coaches will set up email reminders and text message alerts through MyFitnessPal or possibly ANNIE (does not require a smart phone).

In prior deployments of E-LITE, patients required an initial 1-hour orientation, biweekly templated messages (2 minutes/message), and ad-hoc counseling sessions 2 times per month (7 minutes/session). Based on these estimates, a 1-FTE coach could conservatively manage 450 patients over the course of a year. This centralized, off-site staffing approach is not only

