Quantifying Costs: Using validated frameworks, we will quantify VA-perspective costs based on A) within-trial costs for implementing the intervention (intervention group only) and B) downstream healthcare utilization (intervention and control).^{76,77} Similar to prior VA studies, study staff will log all time spent monitoring adherence and on general intervention support including 1) lifestyle coach training, 2) individual lifestyle coaching activities (e.g. orientation, responding to ad hoc patient requests), and 3) planning.⁷⁸ Staff time will be converted to costs based on salaries of the staff conducting the intervention using payroll information. Sensitivity analysis will explore alternative staffing models using estimates from US Bureau of Labor Statistics Occupational Outlook Handbook. Time for research-specific activities including consenting and survey assessments will be excluded. All supply and other material costs will be extracted from intervention fidelity tracking data. To assess potential increases or decreases in longitudinal healthcare utilization, we will compare differences in total utilization in the 24-month period following trial enrollment between the intervention and control groups. Healthcare utilization and total payer costs from will be extracted for all encounters using VA's Managerial Cost Accounting data which is an activity-based allocation system based on payroll and all other care-related expenses (eg. supplies, utilities, service contracts) extracted from VA's general ledger, and any claims patients incur for care delivered in the community that is reimbursed by VA. Confidence intervals for any observed differences in healthcare cost between the intervention and control groups will be estimated using bootstrapping, accounting for distributional assumptions for potentially skewed cost data. Costs will be reported in dollars at the time of reporting final results, with earlier years adjusted for inflation using the Consumer Price Index.

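### Identification and outreach belong to the proactive model under test, but no stated cost component captures them, so the budget impact understates rollout cost per user

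*Protocol*

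**What the plan says.** **The model under test.** The primary aim in Protocol Section 3.0 is to "Test the effectiveness of a proactively delivered and pragmatic weight loss intervention". Section 2.1.7 says that the intervention "uses administrative data to remotely identify and recruit patients, enabling centralized implementation". Sections 2.2 and 2.3 likewise present patient identification and the proactive offer as part of the change in care delivery.

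**The outreach work.** Section 5.2.5 says that "we will mail and/or email invitations to enough Veterans to enroll 696 subjects", with re-mailing to non-responders. Under Section 5.3.1, for people who do not opt out, "a research coordinator may telephone to" describe the study, check eligibility and safety, obtain consent and give baseline surveys. Section 5.3.2 adds emails to primary care providers. Section 5.3.3 places this work before allocation: "Participants must have PCP clearance and completed baseline surveys before randomization can occur".

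**The costing.** Section 5.5.6.3 (Quantifying Costs) has two parts: implementation cost within the trial, for the intervention group only, and downstream utilization in both arms. For the first part, "study staff will log all time spent monitoring adherence and on general intervention support including 1) lifestyle coach training", followed by individual coaching and planning. Time is priced at the salaries of the staff who conduct the intervention, supplies are taken from fidelity tracking, and "Time for research-specific activities including consenting and survey assessments will be excluded".

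**The projection.** Sections 5.5.6.3 and 5.6.4 apply cost differences between the arms to the number of patients expected to use the program nationally. The SAP mentions the budget impact analysis in its abstract but gives no costing rules.

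**The concern.** If the program succeeds because someone finds eligible patients and contacts them, a system that adopts it must pay for the finding and contacting. That cost grows with the number of people approached, whereas the projection grows with the number of users. If it is left out, cost per user is too low, and the gap is widest where uptake is poor, because each user then carries the cost of many contacts that led nowhere.

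The budget impact analysis is meant to support a business case for national rollout. Without outreach it would price the coaching and materials, not the proactively offered program named in the primary aim.

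**Working it through.** **Step 1. Look for outreach in each cost component.**

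- *Within-trial cost.* It covers the intervention group only. Outreach also goes to future controls and to people who never enroll. The listed time items do not name it. Research coordinators make the calls (Protocol 5.3.1, SAP Section 3), whereas time is priced at the pay of those conducting the intervention.
- *Supplies.* These come from fidelity tracking. The Fidelity paragraph describes audits of orientations and coach communications, all with enrolled participants. Invitation packets to non-enrollees have no evident place there.
- *Downstream utilization.* This starts after enrollment, so it cannot contain outreach.
- *Between-arm difference.* Outreach precedes randomization and is the same for both arms, so its expected contribution to the difference is zero. In a rollout the alternative is no program and no outreach, so the cost is incremental there.

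No section of the protocol or SAP assigns a cost to identification, invitation, screening calls or provider notification.

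**Step 2. Reproduce the plan's own staffing figure.** Protocol Section 5.3.6.2 reports that in earlier deployments "patients required an initial 1-hour orientation, biweekly templated messages (2 minutes/message), and ad-hoc counseling sessions 2 times per month (7 minutes/session", and concludes that one full-time coach could manage 450 patients a year.

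- Minutes per patient-year, with 26 messages and 24 counseling sessions: 60 + 26 × 2 + 24 × 7 = 60 + 52 + 168 = 280.
- A 2,080-hour working year (assumed; not in the documents) gives 2,080 × 60 = 124,800 minutes.
- Capacity: 124,800 / 280 = 446, close to 450. With 24 messages, 124,800 / 276 = 452.
- Another reading, 6 messages and an 1,800-hour year, gives 60 + 12 + 168 = 240 minutes and 108,000 / 240 = 450.

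On each of these readings, orientation, messages and counseling use up the whole figure. It leaves no time for identification or outreach.

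**Step 3. Direction.** Let *c* be program cost per user, *k* outreach cost per invited Veteran and *u* the share of invitees who become users. Full cost per user is *c* + *k*/*u*. Omitting *k*/*u* understates the cost for any *k* above zero, and by more as *u* falls.

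**Step 4. Illustrative size.** The documents give neither the number invited per enrollee nor staff minutes per contact. Both inputs below are assumptions. Each entry is people contacted × minutes / 280.

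| People contacted per enrollee | 1 min | 3 min | 5 min | 10 min |
|---|---|---|---|---|
| 5 | 1.8% | 5.4% | 8.9% | 17.9% |
| 10 | 3.6% | 10.7% | 17.9% | 35.7% |
| 20 | 7.1% | 21.4% | 35.7% | 71.4% |
| 50 | 17.9% | 53.6% | 89.3% | 178.6% |

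The extremes are 5 and 500 added minutes. If the same staff did this work, patients per full-time post would fall from 446 to between 124,800 / 285 = 438 and 124,800 / 780 = 160. The case of 20 contacts at 3 minutes adds 60 minutes and gives 124,800 / 340 = 367. Outreach above 28 minutes per enrollee adds more than 10%.

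**The case against.** The strongest reply is that the gap rests on silence. The sentence on excluded time names consenting and surveys and says nothing of list generation, mailing or calls. The list of logged activities is introduced as inclusive, so planning or general support might be stretched to cover some outreach. A reader might infer that the plan expressly excludes outreach, that the log is limited to the named items, or that contact time was never recorded. The documents support none of these. They show only that no stated component captures the work.

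Second, Table 3 and Section 5.3.6 itemize the intervention as orientation, videos, self-monitoring and coach access, and the projection refers to the self-directed program. Costing those items is coherent in itself. It does not settle the matter, because the aim and the framework section put proactive identification and offering inside the model.

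Third, part of the outreach is trial recruitment: study information sheets, re-mailing to keep to the recruitment timeline, re-invitation of women to reach an enrollment goal, consent and baseline surveys. This stands. Not every step would recur in a rollout, and the documents do not say which would.

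Fourth, uptake of a trial invitation is an imperfect guide. Trial invitees face exclusions, surveys and an even chance of usual care alone, so dividing by trial uptake could overstate cost per user. This also stands and shapes the fix.

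Finally, the plan already collects Reach counts and foresees alternative staffing models and possible rollout sensitivity analyses. These supply useful inputs, but none of them costs outreach.

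**Conclusion.** The point holds as an omission by scope. Followed as written, the plan carries identification and outreach in no cost component and so understates rollout cost per user. The direction is clear provided that rollout involves some outreach, as the proactive model implies.

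The size cannot be computed from the documents. The range of about 2% to 179% of 280 coach minutes rests wholly on assumed contacts per enrollee and minutes per contact. A reader might settle on one pair of inputs, for example 10 minutes per invitee and 5% to 15% uptake, which gives 10 / 0.15 = 67 to 10 / 0.05 = 200 minutes, or 24% to 71%. Nothing in the documents favors those values. The base of 280 minutes comes from earlier deployments and leaves out training, materials and downstream utilization, so none of these percentages is the effect on total budget impact.

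The matter is confined to a secondary implementation analysis that is done only if the intervention proves effective. It is still worth correcting, because that analysis is the basis for the rollout case.

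**What to change.** In Protocol Section 5.5.6.3, with the matching text in 5.6.4:

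1. State which pre-randomization activities are program costs and which are research. Candidates for program cost are CDW list generation, invitation by mail or email, calls to people who have not opted out, the safety screen and provider notification. Consent, surveys, randomization and re-mailing to meet enrollment targets would be research.
2. Add the program part to the budget impact as a cost per invited Veteran. Convert it to cost per user with the invited and enrolled counts already planned under Reach (Table 6), and an assumed or sampled time per contact.
3. Vary both time per contact and uptake in sensitivity analysis, and say that uptake of a randomized trial may differ from uptake of a directly offered program.

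The cost is protocol wording and a modest amount of analysis. Recruitment began in April 2022, so time per contact may have to be estimated after the fact. The split between outreach and research time within a single call will be approximate, and the reported cost per user will be less favorable. Trial conduct and the co-primary analyses do not change.
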